9.4.4 PLANNED INTERIM ANALYSES

An interim analysis for inferiority will be conducted at 50% and 75% information accrual. This comparison of the primary outcome, failure of drainage, will be compared between the treatment arms with a one-sided test for superiority of the 28 tube compared to the 14 ($\alpha=0.05$).

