8.2 SAFETY AND OTHER ASSESSMENTS

The PI and the study team will meet biweekly to review the study procedures, enrollment (screening and randomization), implementation, protocol deviations, data collection, and adverse events. The biostatistics team will generate monthly reports for the study team which will monitor screening, enrollment, completeness of data for intervention implementation and outcomes, adverse events, and protocol deviations.

A medical monitor will determine the course of action necessary to meet safety goals and objectives. After the first 20 patients are enrolled and randomized, the study statisticians will generate a safety report for medical monitor review. An interim analysis for inferiority at 50% and 75% information accrual (see section 9.4.4: Planned Interim Analysis) will also be conducted. The medical monitor will recommend stopping if there is an increased incidence of procedure related serious complications or deaths in either treatment group that is found to be clinically significant.

Safety endpoints assessed by the study team and medical monitor will include:

- General safety assessments
 - Incidence of unanticipated serious adverse events related to chest tube size
- Thoracostomy tube related safety events
 - Hemodynamic instability post-insertion
 - Need for additional interventions (VATS, thoracotomy, chest tube replacement)
 - Procedure related deaths
 - Empyema
 - Re-accumulation/Recurrent pneumo- or hemothorax
 - Readmission to hospital within 90 days of insertion

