9.2 SAMPLE SIZE DETERMINATION

Aim I

This study is a non-inferiority randomized controlled trial comparing placement of 14 French vs. 28 French chest tubes for hemothorax and hemopneumothorax. We hypothesize the rate of drainage failure to be approximately 7% in the large 28 tube size group. With a sample size of n=126 per group, we will have 80% power to detect a non-inferiority margin difference between the group rates of 8% (allowing up to a 15% rate of drainage failure in the small 14 tube size group; $\alpha=0.05$). In our prior study, we saw a 20% vs 6.7% difference in needing additional procedures for pneumothorax with small vs large catheters but these numbers are based on draining air not blood. Sample size analyses were conducted in PASS 13⁹.

Aim II

Calculations of sample size were based on two-group comparisons of empyema rates. With assumptions of empyema rate is 5% in the retrospective group and 2% in the prospective group, 586 patients in each group are needed to achieve a power of 0.8 with $\alpha=0.05$. To account for potential attrition, we will inflate the number of patients by 10% resulting in a total of 645 patients in the retrospective group and 645 patients in the prospective group. The sample size was calculated by using the PASS 15¹⁰.

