9.4.3 ANALYSIS OF THE SECONDARY ENDPOINT(S)

Length of stay will be compared using Poisson regression with a main effect of group. Post insertion pain and vital signs will be compared using analysis of covariance controlling for pre-procedural pain and vital signs, respectively, with categorical group effect. We will compare rates of re-intervention and readmission using chi-square tests for independence (or Fisher's exact tests) and present our findings using relative risks and 95% confidence intervals.

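### Does the single α = 0.05 for two inferiority looks in section 9.4.4 need a multiplicity boundary, a named test and a formal stopping rule?

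*Combined protocol and SAP*

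**What the plan says.** Section 9.4.4, repeated in the synopsis, is the whole interim plan for Aim I: "An interim analysis for inferiority will be conducted at 50% and 75% information accrual". Drainage failure "will be compared between the treatment arms with a one-sided test for superiority of the 28 tube compared to the 14", with one α of 0.05 in brackets.

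Three other places bear on it.

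- **Section 9.2** sets the size: "With a sample size of n=126 per group, we will have 80% power", with an 8-point margin. "We hypothesize the rate of drainage failure to be approximately 7% in the large 28 tube size group". It does not mention the looks.
- **Section 8.2** places the looks in the paragraph on the medical monitor, who decides what action safety requires. It adds: "The medical monitor will recommend stopping if there is an increased incidence of procedure related serious complications or deaths" (in either group, if judged clinically significant). The safety endpoints listed for the monitor include the need for VATS or a replacement tube, which overlaps the primary outcome.
- **Section 10.1.2** gives the investigator a general right to end the study.

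Section 9.4.2 names a chi-square test for the final comparison of drainage failure. Section 9.4.3 allows chi-square or Fisher's exact test for secondary rates.

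**The concern.** Testing twice at 0.05 normally gives more than a 5% chance of at least one false positive, and 9.4.4 offers neither a spending rule nor a statement that 0.05 applies to each look. The choice of test is not trivial either. At 7%, only 63 × 0.07 = 4.4 events per arm are expected at the first look, and with so few events the chi-square and Fisher tests can disagree. No sentence ties a crossing to an action.

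The worry is therefore threefold: the false-signal rate is unstated, the same data might or might not cross depending on the test, and the 80% power in 9.2 ignores any early stop. At worst, a sound small-bore tube could be abandoned on a chance finding, or the trial could be underpowered.

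**Working it through.** **Inputs.** 7% failure in the 28 Fr arm, 8-point margin, 126 per group (9.2); looks at 50% and 75% information, one-sided 0.05 (9.4.4); 1:1 allocation (6.4). Assumptions: information is counted as patients, so the looks fall at 63 and at 94 or 95 per arm (0.75 × 126 = 94.5); 0.05 applies at each look; the final analysis uses a Wald one-sided 95% upper limit below 8%.

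**1. The plan's own figure.** n = (1.645 + 0.842)² × 2 × 0.07 × 0.93 / 0.08² = 6.18 × 0.1302 / 0.0064 ≈ 125.8, so 126 per group. This matches 9.2. One-sided 0.025 would need 160, so the final test is at one-sided 0.05. Power at 126 is 80.1% by formula and 80.4% by exact binomial calculation, without looks.

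**2. Two looks, normal approximation.** The correlation of the two statistics is √(0.5/0.75) = 0.816. The chance that either exceeds 1.645 when the rates are equal is 7.4%. A common cut-off of 1.84 (p<0.033) gives 5.0%.

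**3. Two looks, binomial calculation at 63 and 95 per arm, 7% in the 28 Fr arm.**

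| Interim rule | False crossing (7% v 7%) | Net power if every crossing stops | Crossing at 15% v 7% |
|---|---|---|---|
| Uncorrected chi-square, 0.05 per look | 8.2% | 78.5% | 60% |
| Fisher or continuity-corrected, 0.05 per look | 3.7% | 80.0% | 51% |
| Fisher only if expected count <5, otherwise chi-square, 0.05 per look | 5.9% | 79.7% | 60% |
| Uncorrected chi-square, p<0.033 per look | 4.9% | 79.6% | 51% |

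With the uncorrected chi-square test, the single-look rates are 5.6% and 5.4%, so most of the excess over 5% comes from looking twice. At other common rates (63 and 94 per arm), the chi-square and continuity-corrected figures are 8.7% and 2.8% at 5% failure, and 7.6% and 4.5% at 10%.

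**4. If 0.05 is the total.** Splitting it as 0.025 + 0.025 gives 3.8% with the uncorrected chi-square test and 1.7% with Fisher's exact test.

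**5. What a false crossing costs.** With the chi-square rule, 8.2% of equal-rate trials cross, but power falls by only 80.4 − 78.5 = 1.9 points. The other 8.2 − 1.9 = 6.3 points are trials that would not have shown non-inferiority anyway. With Fisher's exact test the loss is 80.4 − 80.0 = 0.4 points.

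**6. Final type I error.** Non-inferiority is claimed only at the end. A stop for inferiority can remove trials from the set that make the claim and can never add one, so the error rate at the margin cannot rise.

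**7. What a stricter cut-off buys.** Moving the chi-square test to p<0.033 saves 8.2 − 4.9 = 3.3 points of false signal. It costs 60.3 − 51.5 = 8.8 points of detection at 15% versus 7%, and 87.3 − 82.5 = 4.8 points at 20% versus 7%.

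**The case for a change.** The best case for a change is that the open choice of test has consequences. Suppose the first look shows 4/63 failures with 28 Fr and 10/63 with 14 Fr. The uncorrected statistic is (6/63) / √(0.1111 × 0.8889 × 2/63) = 0.0952/0.0560 = 1.70, which crosses 1.645. Fisher's one-sided p is 0.077, which does not. Over both looks, the choice more than doubles the false-signal rate (3.7% to 8.2%) and moves detection at the margin by about 9 points. The serious-complication sentence in 8.2 is not tied to this test, so prespecification would protect against choosing the test after seeing the data, and it would cost only a sentence.

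The omission is real and the figures are right. Three things limit it. First, 9.4.2 already names chi-square for this outcome, Fisher's exact test appears only for secondary rates, and nothing says the test will be chosen after the data are seen. Second, the looks sit within the medical monitor's safety remit in 8.2, so they read most naturally as advice to a person weighing all the evidence; a borderline result such as the example would be judged on its merits under either test. Third, the 3.7% to 8.2% range holds only for 0.05 at each look and 7% in both arms.

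**Conclusion.** No change to the plan follows. The detail missing from 9.4.4 is of a kind that analysts fill sensibly: the chi-square test already named for drainage failure, at one-sided 0.05 on each look, reported to the medical monitor. On that reading, the two-look false signal is about 8% if both arms fail at 7%, an acceptable price for harm monitoring. Testing against zero difference is likewise a reasonable choice for that purpose.

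Neither of the trial's main statistical properties is damaged. The non-inferiority type I error is not inflated. The 80% power is not shown to be wrong: it would be 78.5% to 80.0% under the rules examined, and only if every crossing stopped the trial, which the plan does not say. The one substantive alternative, p<0.033 with the uncorrected chi-square test, gives up more detection of a worse tube than it saves in false signals and is a matter of preference. The conclusion assumes that patients are the unit of information and that no non-inferiority claim is made at an interim look, which fits the inferiority-only wording of 9.4.4.

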10 SUPPORTING DOCUMENTATION AND OPERATIONAL CONSIDERATIONS

10.1 REGULATORY, ETHICAL, AND STUDY OVERSIGHT CONSIDERATIONS

10.1.1 INFORMED CONSENT PROCESS

The IRB approved informed consent form (ICF) will adhere to ICH GCP guidelines and comply with the United States Code of Federal Regulations as detailed in 21 CFR §50.25 and the Declaration of Helsinki.

Once eligibility has been confirmed, an investigator/research coordinator will approach each patient or legally authorized representative (LAR) to explain the nature of the study, its purpose, expected duration, alternative forms of therapy available, benefits and risks of study participation. Patients who are GCS = 15 will be approached prior to thoracostomy tube insertion for study consent. Patients with GCS <15 will either be consented by LAR or approached for self-consent if mentation normalizes within 24 hours of tube insertion. Where consent has been obtained from a LAR; the patient will be approached for consent if the investigator later deems the patient GCS = 15 during the study period.

It is expected that most patients/ LARs will be approached in either the emergency room or intensive care unit for consent. After this explanation and before enrollment, the patient or authorized legal representative will be given ample time and opportunity to read the consent form. Patients/LARs who choose to participate will voluntarily sign and date the form in the presence of the investigator/research coordinator.

It will be pointed out to the patient/LAR that they can refuse to participate in the study or withdraw from the study at any time without prejudice to further care and treatment.

The patient/LAR will be given a copy of the signed and dated informed consent form. The acquisition of informed consent will be documented in the patient's medical records.

Patients/LARs will be informed of any significant new finding which arises during the course of study participation that may affect their decision to continue participation.

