1.3 SCHEDULE OF ACTIVITIES (SOA)

Table 1: Schedule of Activities

Study Requirement	Screening	Treatment Period		Follow Up
		Day 0	Day 1 – Discharge	
Eligibility Criteria	X			
Informed Consent ^a	X			
Demographics and Baseline Injury Characteristics	X			
Randomization		X		
Pain Scores	X	X		
Collect Barrier Precautions Data ^b & Antibiotic status		X		
Thoracostomy Tube Placement		X		
Vital Signs ^c	X (pre-placement)	X (post-placement)		
Hematologic, Chemistry and Coagulation Panel Labs	X			
Arterial Blood Gas Data (if applicable)	X			
Toxicology ^d	X			
Injury Severity Score	X			
Measurement of Chest Tube Drainage		→		
Record Date & Time of PTX/HTX or HPTX Resolution ^e		→		

^a Patients who are GCS = 15 will be approached for consent prior to tube insertion. Patients who are GCS <15 will be approached (or their Legally Authorized Representative (LAR) will be approached) within 24 hours of insertion. If an LAR was used for initial consent, the patient will be consented if and when they become GCS = 15 within the follow up period of the study.

^bBarrier precautions recorded include hand hygiene, cap, gown, gloves, mask and thyroid drape

^cAssessed 5 minutes before and after insertion of thoracostomy tube

^dSerum and urine toxicology will be screened for ethanol, amphetamines, barbiturates, benzodiazepines, cocaine, marijuana and opiates only if it is done as standard of care treatment for that patient.

^eRadiologist-confirmed resolution of pneumothorax (PTX), hemothorax (HTX) and hemopneumothorax (HPTX)

Study Requirement	Screening	Treatment Period		Follow Up Day 90
		Day 0	Day 1 – Discharge	
Collect Data on Thoracostomy Tube Misplacement, Air Leak, & Migration				→
Collect Data on Additional Thoracostomy Tubes				→
Assess for Empyema and Fibrothorax				→
Collect Operative Interventions data ^f				→
Record Critical Care and Hospital Stay Parameters ^g				X
Survival				X
Hospital Readmissions				X
Adverse Events/ Serious Adverse Events				→

^fRefers to video-assisted thoracoscopic surgery (VATS), thoracotomy or thoracostomy tube replacement

^gHospital length of stay (days), ICU stay (days), Mechanical ventilation days

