5.2 EXCLUSION CRITERIA

- The patient is incarcerated
- The patient is known to be pregnant
- The patient is hemodynamically unstable, requiring emergent chest tube placement (in <10 minutes from evaluation).
- The patient will have more than one chest tube placed at the time of enrollment.

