5.3 SCREEN FAILURES

Screen failure patients for this study are those who choose to withdraw from the study or who are discovered to meet exclusion criteria after enrollment.

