6 STUDY INTERVENTION

6.1 STUDY INTERVENTION(S) ADMINISTRATION

Screened subjects eligible for study participation will have their inclusion/exclusion criteria verified by an investigator. The subject will be approached for consent by the research staff and enrolled. Subjects with suspected pneumothorax alone will receive either a small bore (14 Fr) or large bore (28 Fr) tube chosen based on physician preference. Subjects with suspected hemothorax or hemopneumothorax will be randomized to receive either a small or large bore chest tube.

Enrolled subjects will have their thoracostomy tube placement procedure observed and verified by an investigator listed on this protocol. The training level of the individual performing the procedure will be recorded. Maximum barrier precautions for this study will be used during the placement procedure for all prospective subjects. Maximum barrier precautions for this study will be defined as the correct use of proper hand hygiene, a cap, surgical gown, sterile gloves, mask, and a thyroid drape. The institutional standard of care thoracostomy tube Practice Guidelines will be followed.

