6.4 MEASURES TO MINIMIZE BIAS: RANDOMIZATION AND BLINDING

We will use stratified permuted block randomization with random block sizes to allocate patients in a 1:1 allocation to the 14 or 28 tube sizes. The randomization lists will be generated by a study statistician using SAS Enterprise Guide version 6.1 and stratified by location (Emergency Department and Surgical & Trauma ICU). Randomization lists will be provided to the study coordinator and another study team member not affiliated with clinical care and assessments to place the allocations into number opaque envelopes. These envelopes will be pulled sequentially by the surgeon or study team as a patient is deemed provisionally eligible for the study preserving allocation concealment. The ID of the envelope is recorded in the patient's research record.

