9.4 STATISTICAL ANALYSES

9.4.1 GENERAL APPROACH

All analyses for this randomized trial will follow the intention to treat principle with an additional per protocol analysis given the non-inferiority hypothesis. We will first compare the baseline characteristics of the patients by group to assess for statistically significant or clinically meaningful imbalances. If either exists, these factors will be taken into account in sensitivity analyses for the primary and secondary outcomes.

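### Some GCS <15 patients can be randomised and given their tube before consent, and the screen-failure definition with an undefined ITT set leaves open whether they can then leave the comparison

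*Combined protocol and SAP*

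**What the plan says.** **Order of events.** Footnote a, under both the schema (1.2) and the Schedule of Activities (1.3), has GCS = 15 patients approached before insertion. For the others it says: "Patients who are GCS <15 will be approached (or their Legally Authorized Representative (LAR) will be approached) within 24 hours of insertion". Section 10.1.1 says: "Patients with GCS <15 will either be consented by LAR or approached for self-consent if mentation normalizes within 24 hours of tube insertion". It also places the consent discussion ahead of enrolment: "After this explanation and before enrollment, the patient or authorized legal representative will be given ample time and opportunity to read the consent form". Under section 6.4 the allocation envelopes are "pulled sequentially by the surgeon or study team as a patient is deemed provisionally eligible for the study", with no condition that consent comes first. Section 6.1 gives a different order, with no exception for GCS <15. After eligibility is verified, "The subject will be approached for consent by the research staff and enrolled", and randomisation of hemothorax and hemopneumothorax patients is described after that.

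**Who stays in.** Section 5.3: "Screen failure patients for this study are those who choose to withdraw from the study or who are discovered to meet exclusion criteria after enrollment". Section 9.4.1: "All analyses for this randomized trial will follow the intention to treat principle", with a per-protocol analysis added. Section 9.3, on analysis populations, only restates the eligible population and defines neither the ITT nor the per-protocol set. No section says whether a randomised patient who refuses deferred consent, withdraws or becomes a screen failure is analysed, dropped or replaced.

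**Related text.** Exclusion 4 in section 5.2 reads: "The patient will have more than one chest tube placed at the time of enrollment". Section 7.1 keeps a patient whose tube is replaced for poor drainage and records this as an outcome.

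**The concern.** ITT protects a randomised comparison only if membership of the analysed set cannot depend on what happened after allocation. Where consent follows insertion, the patient or representative decides when the tube size, and up to a day of its performance, can already be known. Withdrawal, which 5.3 also labels a screen failure, is not confined to the first day. If such patients drop out of the analysis, the loss can be related both to arm and to early drainage.

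In a non-inferiority trial the direction matters. Losing patients who failed, or were heading for failure, on the 14 Fr tube narrows the observed difference and favours a non-inferiority conclusion. With about 9 failures expected per arm at the planning rate (7% of 126 = 8.8), a handful of patients carries weight.

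**Working it through.** **Inputs from the documents.** Sections 9.2 and 8.1: 126 per arm, 7% failure with the 28 Fr tube, margin 8 points (15% for the 14 Fr tube at the margin), alpha 0.05, power 80%. Section 9.4.2: a 95% upper confidence limit, read as one-sided.

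**1. The plan's own figure.** With equal true rates and an unpooled normal approximation,

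n = (z₀.₉₅ + z₀.₈₀)² × 2p(1 − p) / margin² = (1.645 + 0.842)² × 2 × 0.07 × 0.93 / 0.08² = 125.8, rounded up to 126.

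The stated size reproduces at one-sided 0.05. One-sided 0.025 would need 160.

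**2. Effect of losing failures after allocation.** Take the truth at the margin: 15% v 7%, so expected failures are 18.9 v 8.8. The chance of declaring non-inferiority is

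Φ[(0.08 − d) / SE − 1.645], SE = √[p₁(1 − p₁)/n₁ + p₂(1 − p₂)/n₂],

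where d is the difference in the analysed set. Removing k failures from the 14 Fr arm only gives p₁ = (18.9 − k)/(126 − k), with p₂ = 0.07 and n₂ = 126.

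| k removed | p₁ | d (points) | False non-inferiority |
|---|---|---|---|
| 0 | 15.0% | 8.0 | 5.0% |
| 1 | 14.3% | 7.3 | 7.1% |
| 2 | 13.6% | 6.6 | 9.9% |
| 3 | 12.9% | 5.9 | 13.6% |
| 4 | 12.2% | 5.2 | 18.4% |

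For k = 1: SE = √(0.1432 × 0.8568/125 + 0.07 × 0.93/126) = 0.0387, and Φ(0.0068/0.0387 − 1.645) = 0.071.

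**3. Loss from both arms.** Removing the same share of failures from each arm also shrinks the difference. A share of 5%, 10% or 20% gives false non-inferiority of 5.9%, 7.0% or 10.0%. At 10% this is about 1.9 failures from the 14 Fr arm and 0.9 from the 28 Fr arm.

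**4. Single-result view.** One-sided 95% Wald upper limits, with the 14 Fr arm first:

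| Failures | Limit (points) | Against the 8-point margin |
|---|---|---|
| 13/126 v 9/126 | 9.02 | fails |
| 12/125 v 9/126 (one lost, 14 Fr) | 8.20 | fails |
| 11/124 v 9/126 (two lost, 14 Fr) | 7.37 | passes |
| 11/124 v 7/124 (two lost, each arm) | 8.64 | fails |

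A reversal is possible, but from this starting point it takes two failures lost from one arm and none from the other.

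**5. Loss unrelated to outcome.** Dropping 5% or 10% of each arm at random lowers power from 80.1% to 78.3% or 76.3%. Keeping 126 analysable would need 133 (126/0.95) or 140 (126/0.90) randomised per arm. The Aim I total of 252 is exactly 2 × 126 and has no such allowance.

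The losses in steps 2 to 5 are assumptions. The documents give neither the share of GCS <15 patients nor a refusal rate.

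**The case against.** **The sequence is not settled.** The sentence in 10.1.1 sets no time for a representative's consent; its 24-hour clause concerns self-consent. The Schedule of Activities lists consent under Screening and randomisation under Day 0, and 6.1 puts consent first. This stands, to the extent that one cannot say every GCS <15 patient is treated before consent. Footnote a and 6.4 still allow it for some.

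**A label is not an exclusion rule.** Section 5.3 does not say that screen failures leave the analysis, and 9.4.1 states ITT. This also stands: there is a conflict and a gap, not a declared exclusion. But the term normally denotes people who never entered the trial, and nothing in 9.3 overrides that reading.

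**Exclusion 4.** A reader might infer that a patient whose first tube drains badly, and who has a second before deferred consent, is excluded for having two tubes at enrolment, so that primary-outcome failures are removed. The documents do not support this as stated:
- The criterion speaks of tubes to be placed, and sections 4.1 and 6.2 make both enrolment and insertion day 0. It reads naturally as tubes planned at the first procedure.
- Section 7.1 keeps patients whose tube is replaced.
- Section 4.1 defines retained hemothorax only after 72 hours, so a second tube within 24 hours may not be a primary event.

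What remains is that 7.1 does not say it covers a patient who is not yet consented.

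**The size is hypothetical.** Correct. Losses unrelated to outcome mainly cost power, and the reversal in step 4 needs a one-sided pattern of loss.

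**Conclusion.** The point holds in a limited form. Footnote a and 6.4 let some GCS <15 patients be randomised and treated before consent is sought, contrary to the order in 6.1. The screen-failure definition in 5.3 conflicts with ITT, and 9.3 does not resolve the conflict. Refusal of deferred consent and withdrawal are the main routes by which patients could leave the comparison with their tube and early course known.

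The possible effect is material at this sample size: false non-inferiority rises from 5% to about 7-18% if 1 to 4 failures are lost from the 14 Fr arm only, and to about 7% if 10% of failures are lost from both arms. These figures assume true rates of 15% v 7%, an unpooled Wald test at one-sided 0.05, and losses confined to failures. They illustrate sensitivity and do not forecast bias. The documents do not show that early failures will be removed, nor that the trial's conclusion would reverse.

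**What to change.** - **5.3:** limit screen failure to patients for whom no envelope was opened.
- **9.3:** define the ITT set as all randomised patients, analysed as allocated, whose data may be used. Include those who withdraw (data up to withdrawal) and those later found ineligible. Define the per-protocol set alongside it.
- **Reporting:** give by arm, with reasons, the number of opened envelopes without later consent and the number of withdrawals. Add a sensitivity analysis over a range of assumed failure rates for these patients, such as a tipping-point analysis. The extreme case alone (every such 14 Fr patient a failure, every such 28 Fr patient a success) says little: three such 14 Fr patients turn 9 v 9 into 12 v 9, whose limit at 126 per arm is 8.10 and already fails.
- **5.2:** state that exclusion 4 is judged on information available before the envelope is opened, consistent with 7.1.
- **1.2, 1.3, 6.1, 6.4 and 10.1.1:** reconcile the order of consent, randomisation and enrolment for GCS <15 patients.

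The cost is protocol wording and one extra analysis; 6.4 already records envelope IDs. The small downside is that a few ineligible or withdrawn patients stay in the ITT set, which the planned per-protocol analysis complements.
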